3. STUDY DESIGN

3.1.1

Participants

99 stroke patients with dysphagia after an acute/subacute unilateral hemispheric infarction, presenting at Beth Israel Deaconess Medical Center (BIDMC) will be prospectively enrolled, if eligible, into the study. All stroke patients admitted to our hospital receive a standardized dysphagia screening using a bedside water swallow test and are referred for a swallow evaluation to a speech and language pathologist (SLP) if suspected of having dysphagia. Those with moderate to severe dysphagia (PAS ≥ 4) on a standardized videofluoroscopic swallowing (VFSS) evaluation will be invited for participation if they fulfill all study criteria. The patient as well as the SLP will be blinded to the stimulation allocation. Subjects will be randomly assigned to the two intervention or sham groups using PROC PLAN in SAS using a blocking scheme with block size of 6. Subjects will be stratified based on their baseline PAS score (4-6 vs. 7-8) before randomization to the three treatment groups.

3.1.2

Outcomes

Primary Efficacy Outcome: Penetration-Aspiration Score [PAS]: This is a validated 8 point ordinal scale that quantifies penetration and aspiration events observed during VFSS. Since aspiration after stroke is a major predictor of prolonged dysphagia and leads to dietary restrictions, increases the risk of pneumonia and need for tube feeding, this scale will be a relevant measure of swallow status. We have adopted a cut off PAS score ≥ 4 for study enrolment, as minor degrees of penetration can be seen in normal individuals. An average PAS score will be computed based on 5 swallows but if a specific bolus presentation is withheld due to safety concerns, the missing value will be replaced with the worst score (8) for that item.

Primary Safety Outcome: The major safety outcome measures will be **seizures, neurological and motor deterioration or stroke specific mortality** during the period of active stimulation. In light of our small sample size and low expected number of adverse events, we will rely on data from historical cohorts to derive our cut-off numbers for study suspension.

a. Seizures: We expect that a seizure provoked by tDCS would occur during the stimulation session and not thereafter. However, we will analyze the incidence of seizures during the 5 days of active stimulation since excitability changes from tDCS can be prolonged.

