b. Neurological and Motor Deterioration: We will only include neurological deterioration not due to a new stroke, hemorrhagic transformation, or a coexisting encephalopathy. Deterioration will be defined as an increase in the NIHSS by ≥ 4 points between each successive day during active or sham stimulation. NIHSS score will be computed at the bedside by an investigator certified in its performance. Similarly motor deterioration for an individual patient is defined as a ≥ 2 point worsening from baseline on the NIHSS motor sub-item score for a given limb.

c. Swallowing Deterioration: We will record a FOIS score on day 3 of our protocol to assess any deterioration of swallowing with the allocated intervention (tDCS or sham). To minimize

radiation exposure VFSS will not be routinely used for this interim assessment. Subject with ≥ 3 point decrease in FOIS, will undergo an interim VFSS to obtain an interim PAS score. Swallowing deterioration will then be defined as an increase in the PAS score ≥ 2 points compared to baseline score based on this interim assessment not due to other confounding factors outlined above.

d. Stroke specific mortality: Deaths due to direct consequences of brain injury such as brain edema or seizure will count for stroke specific mortality, but not deaths from recurrent ischemic events, hemorrhage, pneumonia, cardiac events, and infections. All deaths will be reported to DSMB who will determine if the death is a possible consequence of tDCS or not.

e. Non serious events such as headaches, skin erythema, fatigue and visual perceptual changes will be tabulated to assess patient tolerability but will not be used as primary safety outcome measures due to their subjective nature. The seriousness of any unexpected adverse events such as a serious skin burn will be promptly reported to the DSMB

Secondary Outcomes: We will use 3 outcomes that assess swallowing physiology, 1 outcome that provides functional (dietary) measure of oral intake, and 3 major safety outcomes.

1. Outcomes of Swallowing Physiology:

a) Pharyngeal Constriction Ratio (PCR): PCR is a measure of the pharyngeal area visible in the lateral radiograph view at the point when a bolus is held in the oral cavity divided by the pharyngeal area at the point of maximum pharyngeal constriction during the swallow.

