b) Hyoid, Laryngeal, and Pharyngeal excursion (HLPE): we will measure the actual excursion of these structures and landmarks from their resting point to maximal excursion. Hyoid, laryngeal and pharyngeal excursion are all important and semi-independent movements that close off the airway, shorten the pharynx, and open the upper esophageal sphincter, and thus are important variables to measure.

c) Pharyngeal Delay Time (PDT): will provide a temporal measure of the briskness of the swallow onset. We define PDT as “the time in centiseconds that the bolus is present in the hypopharynx before the swallow is triggered”. PDT will be measured from the time the bolus first passes the intersection of ramus of mandible and base of tongue, until the swallow begins - as seen by the final excursion of the hyoid bone associated with the swallow.

2. Dietary Outcome: Functional Oral Intake Scale [FOIS]: An important consequence of dysphagia is a compromised and altered diet. FOIS is a functional outcome that provides a validated measure of diet level. It has been tested and validated in stroke population and demonstrated to be sensitive to changes in swallowing functions in acute stroke patient. FOIS is an ordinal scale ranging from 1 (worst) to 7 (normal oral diet). It is easy to use and does not require specific training. It will be collected at four time points: 1) prior to initiating tDCS/sham stimulation (same day); 2) after the fifth session of tDCS/sham; 3) after the last session of tDCS/sham stimulation; and 4) by telephone at 1 month after the last stimulation session using a standardized questionnaire.

3.1.3

Protocol for Swallowing Evaluation

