All participants will undergo 3 bedside swallowing evaluation and 2 standardized videofluoroscopic studies (VFSS) to further quantify dysphagia severity. The VFSS will be conducted by the SLPs at BIDMC according to established protocols. The first VFSS evaluation will occur on the day of first tDCS/sham stimulation session and the second evaluation will occur on the last (5th) day of stimulation. Prior to initiation of this project, the participating SLPs at BIDMC will undergo intensive training sessions with [name] (Boston University Medical Center) so that they can reliably detect deep penetration up to the vocal cords or aspiration (PAS score ≥ 4) on VFSS; patients will be enrolled if their PAS score ≥ 4 on at least one swallow. The SLP at BIDMC will not assign PAS scores which will be done by [name] team at their laboratory in Boston University Medical Center (BUMC). The de-identified and coded VFSS will be transferred electronically using a secure file transfer system on the same day to BUMC for detailed analysis and scoring. The lab at Boston University will be alerted immediately and will analyze the studies promptly to assess whether the PAS scores meet criteria for study enrolment. The patient will be viewed in the lateral plane for most swallows, but one swallow will be viewed in the anterior-posterior plane for asymmetry. The order of presentation will not be randomized but given in an incremental way due to the uncertainty about patient's swallowing status and for safety, as outlined below:

In Lateral view: One 5 ml Nectar Varibar Swallow, One 5ml Varibar pudding, 3 Varibar Thin Swallows: 5 ml thin liquids x1, 10 ml thin x 1, 30 ml thin x1;

10 ml & 30 ml thin liquids boluses are given only if no other boluses are aspirated

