 - d. a swallowing deterioration for an individual patient is defined as follows: A FOIS change from baseline of ≥ 3 points will trigger a repeat, interim swallowing assessment; swallowing deterioration will then be defined as an increase in the PAS score ≥ 2 points compared to baseline score based on this interim assessment. The stopping rule for a swallowing deterioration is:
 - i. pause/stop enrollment in a dose if 5/10 or 8/20 in that dose exhibit swallowing deterioration;
 - ii. Pause/stop all enrollment if at least 8/20 or 13/40 patients in both active doses combined swallowing deterioration; note that the probability for these rules is based on the following assumptions and on the binomial distribution:
 1. we assume the natural history of the condition yields probability of swallowing deterioration of 20%;

2. probability of stopping the study for safety, if this is the true probability, using the above stopping rules, is $\leq 5\%$;
 3. thus if the stopping rule is met, odds are that true rates are higher than 20%;
- e. a neurological deterioration for an individual patient is defined as a ≥ 4 point worsening from baseline on the NIHSS global impairment score. The same stopping rule for swallowing deterioration will be applied to neurological deterioration.
 - f. A limb deterioration for an individual patient is defined as a ≥ 2 point worsening from baseline on the NIHSS motor score for a given limb. The same stopping rule for swallowing deterioration will be applied to limb deterioration.

These stopping rules will serve as a guideline, not an absolute end-point, for the DSMB to consider stopping the trial.

All reported AEs and AEs considered by the study investigator to be treatment-related (having a relationship of at least possibly study intervention) will be tabulated for all patients who have received any amount of intervention. Tabulations of serious adverse events will be provided. As part of the AE and serious AE tabulations, the incidence of neurological and swallowing deteriorations will be provided. At regularly scheduled meetings the DSMB will be provided with a copy of all SAE Reports. In addition, the DSMB will be notified of any reportable SAEs as soon as possible in between meetings. Any additional information necessary to evaluate the continued safety of all patients enrolled in this trial will also be provided.

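### The swallowing stopping rule cannot register an event in patients with baseline FOIS 1-3 or baseline PAS above 6, though it counts them, and its 5% limit holds only per look

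*Combined protocol and SAP*

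**What the plan says.** The event has two steps. Under section 3.1.2(c), a patient whose day 3 FOIS shows a "≥ 3 point decrease in FOIS, will undergo an interim VFSS to obtain an interim PAS score". Section 6.1.1, item 6(d), uses the same gate but says only that FOIS changes, without a direction. At the interim assessment, "swallowing deterioration will then be defined as an increase in the PAS score ≥ 2 points compared to baseline score".

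The scales are bounded: "FOIS is an ordinal scale ranging from 1 (worst) to 7 (normal oral diet"), and for PAS, "This is a validated 8 point ordinal scale that quantifies penetration and aspiration events observed during VFSS". Neither section gives another criterion for patients who start near the bad end of either scale.

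Severe patients are expected. Section 3.1.1 states: "Subjects will be stratified based on their baseline PAS score (4-6 vs. 7-8) before randomization to the three treatment groups". Section 3.1.3 admits on a single swallow ("patients will be enrolled if their PAS score ≥ 4 on at least one swallow"), while the efficacy outcome is the mean of five swallows, with withheld boluses scored 8. Withholding is planned: "10 ml & 30 ml thin liquids boluses are given only if no other boluses are aspirated".

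The boundaries are 5/10 or 8/20 within a dose, and 8/20 or 13/40 over both active doses. The denominators are not restricted. Item 6(d) assumes a natural-history probability of 20% and states that, at that rate, the chance of stopping under these rules is at most 5%.

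**The concern.** A trigger that some patients cannot set off, whatever happens to them, is a trigger for the remaining patients only. Here the excluded patients are those with the worst swallowing at entry, and this is the only numerical stopping rule for swallowing. Counting them in the denominators means that a harm spread evenly over all patients shows up at less than its true frequency, so a boundary is crossed less often than the stated counts suggest.

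The size of the loss depends on two things that the plan leaves open: the share of patients who cannot meet the definition, and whether the 20% describes all patients or only those who can meet it. It is also unclear which PAS is compared with baseline, and this decides who is excluded.

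A second, separate matter is the 5%. It is stated for the rules together, but each rule is applied at two sample sizes.

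**Working it through.** **1. Who can be an event.** Inputs: scale limits (section 3.1.2) and thresholds (section 6.1.1, item 6(d)).
- FOIS: baseline − 3 ≥ 1 requires baseline ≥ 4. Baselines 1, 2 and 3 are excluded.
- PAS: baseline + 2 ≤ 8 requires baseline ≤ 6. Exactly 6 still qualifies.

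**2. Which PAS.** On a worst-swallow score, the whole 7-8 stratum is excluded. On the five-swallow mean, with the 10 ml and 30 ml boluses withheld and scored 8, the mean is (a + b + c + 16)/5, where a, b and c are the other three scores. It exceeds 6 when a + b + c ≥ 15. Scores 7, 7, 1 give 31/5 = 6.2 (excluded); 8, 1, 1 give 26/5 = 5.2 (able to be an event).

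**3. The plan's 5%, reproduced.** Exact binomial tails at 20%:

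| Boundary | Probability |
|---|---|
| 5/10 | 3.28% |
| 8/20 | 3.21% |
| 13/40 | 4.32% |

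Each is below 5%. Over two looks, the chance is P(cross at look 1) + P(not at look 1, cross at look 2):
- Per dose (5/10, then 8/20): 3.28% + 1.94% = 5.22%.
- Combined (8/20, then 13/40): 3.214% + 2.854% = 6.07%.

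**4. Loss of sensitivity.** Let f be the share who cannot meet the definition. It is not in the documents, so a range is assumed. Figures are single-look; each patient is taken to be in the excluded group independently with probability f.

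*20% is the all-patient rate of the two-step event.* The figures in step 3 are unchanged. If the overall observed rate doubles to 40%, 8/20 is crossed 58% of the time and 13/40 87%, with no loss (possible while f ≤ 60%). If instead harm adds 20 points to every patient's risk but shows only in those who can be events, the observed rate is 0.20 + 0.20(1 − f):

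| f | Observed rate | 8/20 | 13/40 |
|---|---|---|---|
| 0% | 40% | 58% | 87% |
| 10% | 38% | 51% | 81% |
| 20% | 36% | 44% | 73% |
| 30% | 34% | 36% | 64% |
| 50% | 30% | 23% | 42% |

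*20% is the rate only in patients who can be events, and it doubles to 40%.* The observed rate is 0.40(1 − f):

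| f | Observed rate | 8/20 | 13/40 |
|---|---|---|---|
| 0% | 40% | 58% | 87% |
| 10% | 36% | 44% | 73% |
| 20% | 32% | 29% | 53% |
| 30% | 28% | 17% | 32% |
| 50% | 20% | 3% | 4% |

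Holding the excluded number fixed instead of random changes the f = 30% row to 15.0% and 30.5%.

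**The case against.** The strongest reply is textual. Item 6(d) defines swallowing deterioration as the two-step event and then uses that same term for the 20%, without restricting the rate or the counts. Read so, 20% is the all-patient rate, the boundaries behave as designed, and the second table in step 4 does not apply. This stands as the more natural reading. What remains on it is harm in patients whom the definition cannot reach.

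Next, the rules are guidelines. Under sections 6.1.1 and 6.1.2 the DSMB also receives by-patient listings, FOIS and PAS changes by group, and comparisons of each dose with sham; section 9 allows a recommendation to stop on general safety grounds. A fall from FOIS 3 to 1, or a rise from PAS 7 to 8, would appear in those data. This stands too. A reader might infer that monitoring is blind in severe patients; the documents do not support that. The back-up is only partial, though: change scores share the same floor and ceiling, routine VFSS is done only on days 1 and 5, and scheduled meetings may be yearly.

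The FOIS gate also has a stated reason, that to limit "radiation exposure VFSS will not be routinely used for this interim assessment". That is sound, and nothing here asks to remove it.

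Finally, only the PAS 7-8 stratum is documented. No baseline FOIS distribution is given, and the eligibility criteria are not listed in the text available, so the FOIS side could be small. This is why no single figure for the loss can be given.

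**Conclusion.** The gap is certain: with these thresholds and scale limits, patients at baseline FOIS 1-3 or PAS above 6 cannot be events but are counted. The loss of sensitivity is conditional. On the all-patient reading at f = 30%, a uniform 20-point harm crosses 13/40 64% of the time instead of 87%. If the 20% describes only patients who can be events, a doubling crosses 8/20 17% instead of 58% of the time, and 13/40 32% instead of 87%. The values of f and the uniform-harm scenario are assumptions.

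Two stronger conclusions are tempting and unsupported. One is that the boundaries should be recut for patients who can be events, at a 20% rate. If 20% is the all-patient rate, the true background in those patients is 0.20/(1 − f). At f = 30% (28.6%), a recut 6/14 would be crossed 18.5% of the time with no harm; at f = 50% (40%), a recut 5/10 would be crossed 36.7% of the time. The other is that the 5% limit is wrong outright. It holds at each look and is exceeded modestly over two: 5.2% per dose and 6.1% combined.

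Severity is minor if f is about 10% or less, and should-fix if it is larger.

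**What to change.** 1. In sections 3.1.2(c) and 6.1.1, item 6(d), name the PAS measure compared with baseline (worst swallow or five-swallow mean), and specify a decrease in FOIS in both places.
2. In each DSMB report, give per arm the number able to meet the definition (baseline FOIS ≥ 4 and PAS ≤ 6 on the named measure) beside the event count. Flag the remaining patients in the by-patient listings, so that any FOIS or PAS worsening in them is reviewed directly.
3. Keep the counts 5, 8, 8 and 13. State that the 20% is the all-patient rate of the two-step event. Reset the boundaries only if the sponsor's source shows that it describes patients who can be events.
4. Restate the 5% as a per-look figure, or give 5.2% per dose and 6.1% combined over both looks.

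The cost is wording, one extra line in the DSMB report, and a slightly less favourable stated probability. No patients, tests or radiation are added. The change does not restore a numerical trigger for the flagged patients; no background rate is given from which to set one.

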 - ii) Examining effects of differing doses of anodal tDCS versus sham stimulation on several physiological measures of swallowing, derived from videofluoroscopic swallowing studies;
 - iii) Evaluating durability of any observed effects of tDCS on dietary status as determined by changes in Functional Oral Intake Scale (FOIS) score at study onset and 1 month.
- B) We will assess safety by comparing the anticipated and observed incidence of the following major adverse events in each of the 3 groups: seizures, stroke specific mortality, neurological and swallowing deterioration as measured by changes in NIH Stroke Scale (NIHSS), and FOIS and PAS scores, respectively.

Secondary Aim: To investigate the impact of subject-specific predictors of dysphagia recovery on the outcome of our proposed intervention.

Approach: We will examine differences in the effect size of our intervention across different strata of subject specific-predictors extracted from our pilot model as well as corticobulbar tract (CBT)-lesion load (as a surrogate measure of lesion size and location) by performing a subgroup analysis using regression models.

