tDCS group (high-dose)	tDCS exercises +	tDCS exercises +	tDCS exercises +	tDCS exercises +	tDCS exercises +	
	tDCS exercises +	tDCS exercises +	tDCS exercises +	tDCS exercises +	tDCS exercises +	
Outcome Measures	PAS PCR, HLPE, PDT FOIS NIHSS	NIHSS	NIHSS FOIS	NIHSS	PAS PCR, HLPE, PDT FOIS NIHSS	FOIS

3.1.5

Neuroimaging Analysis

Computation of CBT-lesion load: We will perform functional imaging experiments in 8 healthy volunteers to identify the cortical swallowing centers and use this location as a seed region to identify the corticobulbar tract in a separate group of elderly healthy control subjects that had undergone high resolution DTI. The functional imaging experiment will consist of repeated swallowing trials contrasted with whole hand opening and closing tasks, done at the same frequency as the swallowing tasks. Functional MR images will be acquired with a gradient-echo T2*-weighted MR pulse sequence using our own modification of a sparse temporal sampling method with clustered volume acquisition to overcome imaging artifacts caused by swallowing motion. The voxel clusters of significant activation will be used as a seed region (to identify the cortical origin of the CBT). The second seed region will be defined in the posterior pons. The CBT will be traced from the cortical seed region in the swallowing cortex to the posterior pons regions. Exclusion masks will be drawn in order to exclude fiber projections that are not part of the CBT

Identifying and reconstructing the corticobulbar tract and determining the CBT-lesion load:

We will construct the corticobulbar tract by using the combination of fMRI activation patterns obtained and DTI in 12 healthy control subjects. The DTI scans will be high resolution studies obtained in normal controls, using a single-shot, spin-echo echoplanar imaging sequence with the following parameters: TR=10 seconds, TE=86.9 ms, resolution 2.6x 2.6 x 2.6 mm³, 30

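### Neurological deterioration is a day-to-day NIHSS rise in the primary safety outcome (3.1.2(b)) but a rise from baseline in the stopping rule (6.1.1, item 6(e)); the outcome should use baseline too

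*Combined protocol and SAP*

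**What the plan says.** Section 3.1.2 lists neurological and motor deterioration among the primary safety outcomes during stimulation. Under item (b), neurological deterioration is an NIHSS increase of at least 4 "points between each successive day during active or sham stimulation". Causes are restricted: "We will only include neurological deterioration not due to a new stroke, hemorrhagic transformation, or a coexisting encephalopathy". The same item counts motor deterioration separately, as at least 2 points worse than baseline on the NIHSS motor sub-item for one limb.

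Section 6.1.1, item 6(e), defines the same term for the stopping rule as at least a 4-point "worsening from baseline on the NIHSS global impairment score. The same stopping rule for swallowing deterioration will be applied to neurological deterioration". It does not mention the excluded causes.

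The outcome has two uses. Section 2 (Primary Aim, Approach B) says: "We will assess safety by comparing the anticipated and observed incidence of the following major adverse events in each of the 3 groups", and neurological deterioration is one of those events. Section 3.1.2, introducing the primary safety outcome, adds that "we will rely on data from historical cohorts to derive our cut-off numbers for study suspension".

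The schedule table in section 3.1.4 lists NIHSS on every day from Day 1 to Day 5; the Day 1 and Day 5 cells read "PAS PCR, HLPE, PDT FOIS NIHSS".

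**The concern.** One term has two reference points, and both stand in current text. The other deterioration events do not have this problem. Motor or limb deterioration is measured from baseline in both 3.1.2(b) and 6(f), and swallowing deterioration is measured against baseline in both 3.1.2(c) and 6(d). Only neurological deterioration changes its reference day, although 3.1.2(b) presents the motor rule as similar to it. A drafting slip is the likely cause.

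What is at stake is mainly the final safety result. A comparison of anticipated with observed incidence in each group needs one event definition. If the analysis follows 3.1.2(b) as written, a patient who worsens steadily over the stimulation course is not counted as a neurological deterioration, while a patient who improves and then slips back to the starting score is.

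**Working it through.** The plan gives no figure on this point, so there is none to reproduce. The check compares the two definitions on the planned assessment schedule.

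**Inputs**
- NIHSS once daily on Days 1 to 5 (section 3.1.4 schedule): five scores, 5 - 1 = 4 day-to-day changes.
- Rule A (3.1.2(b)): event if any daily change is 4 or more.
- Rule B (6(e)): event if any later score is 4 or more above baseline.
- Assumptions: baseline is the Day 1 score taken before stimulation, and Rule B applies at any daily assessment. Item 6(e) states no time window.

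**Largest worsening that Rule A cannot flag**

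If no daily change reaches 4, each is at most 3. After k intervals the rise above Day 1 is therefore at most 3 x k:
- Day 2: 3 x 1 = 3 (not an event under Rule B either)
- Day 3: 3 x 2 = 6
- Day 4: 3 x 3 = 9
- Day 5: 3 x 4 = 12

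So Rule A can miss rises from 4 (the smallest that Rule B counts) up to 12. Listing every path of four integer changes from -6 to +3 gives the same maximum, 12. If there were a separate baseline before Day 1, which is an assumption the schedule does not support, there would be five intervals and the maximum would be 3 x 5 = 15.

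**Example paths**

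| NIHSS, Days 1-5 | Largest daily rise | Largest rise above Day 1 | Event, 3.1.2(b) | Event, 6(e) |
|---|---|---|---|---|
| 8, 10, 12, 12, 12 | 2 | 4 | no | yes |
| 8, 11, 14, 17, 20 | 3 | 12 | no | yes |
| 12, 8, 8, 12, 12 | 4 | 0 | yes | no |
| 8, 12, 12, 12, 12 | 4 | 4 | yes | yes |
| 8, 8, 14, 14, 14 | 6 | 6 | yes | yes |

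Rows 1 to 3 show that neither rule contains the other, so 3.1.2(b) is not simply the stricter version. Rows 4 and 5 show that the rules agree when worsening is abrupt and starts from the baseline level. In rows 1 and 2 the 3.1.2(b) column refers to neurological deterioration only: if one limb accounts for at least 2 of the points, the patient is counted under motor deterioration.

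**Why the net effect cannot be computed**

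That would need the rate of neurological deterioration and the day-to-day variability of NIHSS. The documents give neither. The only background rate beside the cut-offs that 6(e) borrows is for another event: "we assume the natural history of the condition yields probability of swallowing deterioration of 20" per cent.

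**The case against.** The strongest reply is that patients are protected either way. Item 6(e) carries its own definition beside its rule. The DSMB table line in section 10 speaks of limb deteriorations, which is the term of 6(f) rather than the motor deterioration of 3.1.2(b), and its order follows the items in 6.1.1. The DSMB count therefore most likely uses 6(e), which flags the 8, 11, 14, 17, 20 path on Day 3. The rules are advisory. The DSMB also sees NIHSS change from baseline by group (section 6.1.2) and by-patient listings (section 6.1.1), and it is to agree the table shells and stopping rules at its organizational meeting (section 7). All of this stands. It limits the risk during the trial, but it does not correct the outcome definition in 3.1.2(b).

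A second reply is that the day-to-day rule has a purpose: with daily stimulation, an abrupt overnight fall is a plausible safety signal even in a patient who had been improving. This also stands, and the fix keeps that count.

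A reader might infer more than the text supports:
- *A 12-point decline would leave no trace in 3.1.2(b).* True only if no limb worsens by 2 points or more from baseline; otherwise it counts as motor deterioration.
- *The stopping rule would miss gradual decline.* Not on the natural reading that the rule uses 6(e).
- *The cause exclusions contradict each other.* Item 6(e) is silent, which may be mere abbreviation: 6(d) likewise omits the qualifier that 3.1.2(c) attaches to swallowing deterioration, "not due to other confounding factors outlined above". The point is unclear, not contradictory.
- *Section 9 makes neurological deterioration the sole formal ground for stopping.* It offers it as one possible ground beside general safety concerns, and 6.1.1 sets rules for other events as well.

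**Conclusion.** The inconsistency is real and should be corrected. Its weight falls on the primary safety outcome rather than on the stopping rule. As written, 3.1.2(b) can leave a rise of 4 to 12 NIHSS points over the five days uncounted as neurological deterioration, and it can count a patient who never exceeds the starting score. Twelve points is a worst case. It rests on one score per day, Day 1 as baseline, and no limb worsening by 2 points.

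How many patients would be classified differently cannot be derived from the documents, and it may be few if deterioration is mostly abrupt. The documents therefore do not support any claim that cut-offs would be crossed or missed at a given rate. This is a definition to settle before the safety data are tabulated, not evidence that monitoring would fail.

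**What to change.** 1. In 3.1.2(b), define neurological deterioration on the same basis as 6(e): NIHSS at least 4 points above the Day 1 score taken before stimulation, at any daily assessment through Day 5. Put the same time window into 6(e).
2. State that this definition serves the final safety analysis, the DSMB tables in section 10 and the stopping count.
3. Report a rise of at least 4 between successive days as a supportive count under its own name, so that an abrupt fall after a session is still seen.
4. State in 6(e) whether the cause exclusions of 3.1.2(b) apply to the stopping count.

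The cost is a wording change in two sections and one extra table row. No new data are needed, because NIHSS is already scheduled daily.
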